50000	20%	10000	5	0.05%	0.0%	0.1%	99.33%	44.7%
50000	20%	10000	4	0.04%	0.0%	0.1%	98.17%	50.0%
50000	20%	10000	3	0.03%	0.0%	0.1%	95.02%	57.7%
50000	20%	10000	2	0.02%	0.0%	0.1%	86.47%	70.7%
50000	20%	10000	1	0.01%	0.0%	0.1%	63.21%	100.0%
50000	10%	5000	250	5.00%	4.4%	5.6%	>99.99%	6.2%
50000	10%	5000	200	4.00%	3.5%	4.6%	>99.99%	6.9%
50000	10%	5000	100	2.00%	1.6%	2.4%	>99.99%	9.9%
50000	10%	5000	50	1.00%	0.7%	1.3%	>99.99%	14.1%
50000	10%	5000	5	0.10%	0.0%	0.2%	99.33%	44.7%
50000	10%	5000	4.5	0.09%	0.0%	0.2%	98.89%	47.1%
50000	10%	5000	4	0.08%	0.0%	0.2%	98.17%	50.0%
50000	10%	5000	3.5	0.07%	0.0%	0.2%	96.98%	53.4%
50000	10%	5000	3	0.06%	0.0%	0.2%	95.03%	57.7%
50000	10%	5000	2.5	0.05%	0.0%	0.2%	91.80%	63.2%
50000	10%	5000	2	0.04%	0.0%	0.1%	86.47%	70.7%
50000	10%	5000	1.5	0.03%	0.0%	0.1%	77.69%	81.6%
50000	10%	5000	1	0.02%	0.0%	0.1%	63.22%	100.0%
50000	10%	5000	0.5	0.01%	0.0%	0.1%	39.35%	141.4%
50000	5%	2500	125	5.00%	4.2%	5.9%	>99.99%	8.7%
50000	5%	2500	100	4.00%	3.3%	4.8%	>99.99%	9.8%
50000	5%	2500	50	2.00%	1.5%	2.6%	>99.99%	14.0%
50000	5%	2500	25	1.00%	0.6%	1.5%	>99.99%	19.9%
50000	5%	2500	12.5	0.50%	0.3%	0.9%	>99.99%	28.2%
50000	5%	2500	2.5	0.10%	0.0%	0.3%	91.80%	63.2%
50000	5%	2500	2.25	0.09%	0.0%	0.3%	89.47%	66.6%
50000	5%	2500	2	0.08%	0.0%	0.3%	86.48%	70.7%
50000	5%	2500	1.75	0.07%	0.0%	0.3%	82.63%	75.6%
50000	5%	2500	1.5	0.06%	0.0%	0.3%	77.70%	81.6%
50000	5%	2500	1.25	0.05%	0.0%	0.3%	71.36%	89.4%
50000	5%	2500	1	0.04%	0.0%	0.2%	63.22%	100.0%
50000	5%	2500	0.75	0.03%	0.0%	0.2%	52.77%	115.5%
50000	5%	2500	0.5	0.02%	0.0%	0.2%	39.35%	141.4%
50000	5%	2500	0.25	0.01%	0.0%	0.2%	22.12%	200.0%
50000	2%	1000	50	5.00%	3.7%	6.5%	>99.99%	13.8%
50000	2%	1000	40	4.00%	2.9%	5.4%	>99.99%	15.5%
50000	2%	1000	20	2.00%	1.2%	3.1%	>99.99%	22.1%
50000	2%	1000	10	1.00%	0.5%	1.8%	>99.99%	31.5%
50000	2%	1000	1	0.10%	0.0%	0.6%	63.23%	99.9%
50000	2%	1000	0.9	0.09%	0.0%	0.6%	59.36%	105.4%

Expected Population medically followed by the enrolled practices	Vaccine coverage	Vaccinated subjects	Subjects with events	Expected Proportion of subjects with ≥ 1 AEI reported	Lower 95%CL	Upper 95%CL	Probability to observe ≥ 1 AEI in the study population	Associated Relative standard error (RSE)
50000	2%	1000	0.8	0.08%	0.0%	0.6%	55.08%	111.8%
50000	2%	1000	0.7	0.07%	0.0%	0.5%	50.35%	119.5%
50000	2%	1000	0.6	0.06%	0.0%	0.5%	43.13%	129.1%
50000	2%	1000	0.5	0.05%	0.0%	0.5%	39.35%	141.4%
50000	2%	1000	0.4	0.04%	0.0%	0.5%	32.97%	158.1%
50000	2%	1000	0.3	0.03%	0.0%	0.5%	25.92%	182.5%
50000	2%	1000	0.2	0.02%	0.0%	0.4%	18.13%	223.6%
50000	2%	1000	0.1	0.01%	0.0%	0.4%	9.52%	316.2%

Table 2 **Exact 95% Confidence Intervals, Relative Standard Error and cumulative probability to observe at least one AEI by week associated with a probability of occurrence of event of 1%**

Week	Expected Population medically followed by the enrolled practices	Cumulative Vaccine coverage after 14 weeks	Cumulative number of Vaccinated subjects	Cumulative number of Subjects reported ≥ 1 AEI	Average Proportion of AEI reported	Lower 95%CL	Upper 95%CL	Cumulative Probability to observe at least one event	Associated Relative standard error (RSE)
1	50000	20%	714	7	1.00%	0.4%	2.0%	99.92%	37.2%
2	50000	20%	1428	14	1.00%	0.5%	1.6%	>99.99%	26.3%
3	50000	20%	2142	21	1.00%	0.6%	1.5%	>99.99%	21.5%
4	50000	20%	2857	28	1.00%	0.7%	1.4%	>99.99%	18.6%
5	50000	20%	3571	35	1.00%	0.7%	1.4%	>99.99%	16.7%
6	50000	20%	4285	42	1.00%	0.7%	1.3%	>99.99%	15.2%
7	50000	20%	5000	50	1.00%	0.7%	1.3%	>99.99%	14.1%
8	50000	20%	5714	57	1.00%	0.8%	1.3%	>99.99%	13.2%
9	50000	20%	6428	64	1.00%	0.8%	1.3%	>99.99%	12.4%
10	50000	20%	7142	71	1.00%	0.8%	1.3%	>99.99%	11.8%
11	50000	20%	7857	78	1.00%	0.8%	1.2%	>99.99%	11.2%
12	50000	20%	8571	85	1.00%	0.8%	1.2%	>99.99%	10.7%
13	50000	20%	9285	92	1.00%	0.8%	1.2%	>99.99%	10.3%
14	50000	20%	10000	100	1.00%	0.8%	1.2%	>99.99%	9.9%
1	50000	10%	357	3	1.00%	0.2%	2.4%	97.23%	52.7%
2	50000	10%	714	7	1.00%	0.4%	2.0%	99.92%	37.2%
3	50000	10%	1071	10	1.00%	0.4%	1.7%	>99.99%	30.4%
4	50000	10%	1428	14	1.00%	0.5%	1.6%	>99.99%	26.3%
5	50000	10%	1785	17	1.00%	0.6%	1.5%	>99.99%	23.6%
6	50000	10%	2142	21	1.00%	0.6%	1.5%	>99.99%	21.5%
7	50000	10%	2500	25	1.00%	0.6%	1.5%	>99.99%	19.9%
8	50000	10%	2857	28	1.00%	0.7%	1.4%	>99.99%	18.6%
9	50000	10%	3214	32	1.00%	0.7%	1.4%	>99.99%	17.6%
10	50000	10%	3571	35	1.00%	0.7%	1.4%	>99.99%	16.7%
11	50000	10%	3928	39	1.00%	0.7%	1.4%	>99.99%	15.9%
12	50000	10%	4285	42	1.00%	0.7%	1.3%	>99.99%	15.2%
13	50000	10%	4642	46	1.00%	0.7%	1.3%	>99.99%	14.6%
14	50000	10%	5000	50	1.00%	0.7%	1.3%	>99.99%	14.1%
1	50000	5%	178	1	1.00%	0.0%	3.1%	83.29%	74.6%
2	50000	5%	357	3	1.00%	0.2%	2.4%	97.23%	52.7%
3	50000	5%	535	5	1.00%	0.3%	2.2%	99.54%	43.0%
4	50000	5%	714	7	1.00%	0.4%	2.0%	99.92%	37.2%
5	50000	5%	892	8	1.00%	0.4%	1.8%	99.99%	33.3%
6	50000	5%	1071	10	1.00%	0.4%	1.7%	>99.99%	30.4%
7	50000	5%	1250	12	1.00%	0.5%	1.7%	>99.99%	28.1%
8	50000	5%	1428	14	1.00%	0.5%	1.6%	>99.99%	26.3%
9	50000	5%	1607	16	1.00%	0.6%	1.6%	>99.99%	24.8%
10	50000	5%	1785	17	1.00%	0.6%	1.5%	>99.99%	23.6%
11	50000	5%	1964	19	1.00%	0.6%	1.5%	>99.99%	22.5%
12	50000	5%	2142	21	1.00%	0.6%	1.5%	>99.99%	21.5%
13	50000	5%	2321	23	1.00%	0.6%	1.5%	>99.99%	20.7%
14	50000	5%	2500	25	1.00%	0.6%	1.5%	>99.99%	19.9%
1	50000	2%	71	0	1.00%	0.0%	5.1%	51.01%	118.1%
2	50000	2%	142	1	1.00%	0.0%	3.9%	76.00%	83.5%
3	50000	2%	214	2	1.00%	0.1%	3.3%	88.36%	68.0%
4	50000	2%	285	2	1.00%	0.1%	2.5%	94.30%	58.9%
5	50000	2%	357	3	1.00%	0.2%	2.4%	97.23%	52.7%
6	50000	2%	428	4	1.00%	0.3%	2.4%	98.65%	48.1%
7	50000	2%	500	5	1.00%	0.3%	2.3%	99.34%	44.5%
8	50000	2%	571	5	1.00%	0.3%	2.0%	99.68%	41.6%
9	50000	2%	642	6	1.00%	0.3%	2.0%	99.84%	39.3%

Week	Expected Population medically followed by the enrolled practices	Cumulative Vaccine coverage after 14 weeks	Cumulative number of Vaccinated subjects	Cumulative number of Subjects reported ≥ 1 AEI	Average Proportion of AEI reported	Lower 95%CL	Upper 95%CL	Cumulative Probability to observe at least one event	Associated Relative standard error (RSE)
10	50000	2%	714	7	1.00%	0.4%	2.0%	99.92%	37.2%
11	50000	2%	785	7	1.00%	0.4%	1.8%	99.96%	35.5%
12	50000	2%	857	8	1.00%	0.4%	1.8%	99.98%	34.0%
13	50000	2%	928	9	1.00%	0.4%	1.8%	99.99%	32.7%
14	50000	2%	1000	10	1.00%	0.5%	1.8%	>99.99%	31.5%

Statistical analyses

All data processing and statistical analysis will be performed within the secure IT environment of the Clinical Informatics Research Group, at the University of Surrey. R and SAS Software will be used for the statistical analyses. Statistical analyses will be described in details in a statistical analysis plan, including the methodology to account for the clustering effect.

Coded data will be interpreted by the creation of ontologies allowing to map to case-definitions, where available. However, no in depth descriptions required for case definition will be used such as in clinical trials. Meaning will be inferred from brief clinical coded information.

Sequence of analysis

Interim analysis

Weekly safety report

Weekly safety reports will be generated in order to be able to detect and potentially report any safety concerns in near real time manner. Analyses will be performed overall and by vaccine brand (*Fluarix Tetra* vs. others).

The weekly incidence rates of AEIs within 7 days will be estimated as follows:

- The denominator will consist of the number of subjects vaccinated two weeks before the week of interest
- The numerator will encompass all subjects from the denominator reporting the AEI within 7 days following vaccination with a seasonal influenza vaccine

Final analysis after end of the surveillance period

Analyses of demographics/baseline characteristics

Characteristics of the participating GP practices (Clinical Commissioning Group (i.e. the administrative health division used in England), North/South, Urban/Rural, IMD, number of registered subjects (rounded to the nearest 1000 to avoid the identification of the GP practices) will be tabulated.

Demographic characteristics will be summarized using descriptive statistics:

- Frequency tables will be generated for categorical variables such as gender
- Mean, median, standard deviation, maximum and minimum will be provided for continuous data such as age.

Analyses of the primary objective

All analyses will be carried out overall and by vaccine brand (*Fluarix Tetra* vs. others), by age strata (6 months to 5 years; 6 to 12 years; 13 to 17 years; \geq 18-65 years; $>$ 65 years) and UK CMO-specified risk groups status (at risk/not at risk).

The weekly incidence rates (per 100 subjects) of AEIs within 7 days will be estimated as follows:

- The denominator will consist of the number subjects vaccinated the week before the week of interest (so reaching up to 7 days of follow-up post vaccination during the week of interest) and having received an ADR card.
- The numerator will encompass all subjects from the denominator reporting the AEI within 7 days following vaccination with a seasonal influenza vaccine derived from the ADR card

The cumulative incidence rates (per 100 subjects) of AEIs within 7 days will be estimated as follows:

- The denominator will be the number of subjects vaccinated at any point from study start up to the week before the week of interest (i.e. cumulatively since the beginning of the study) and having received an ADR card.
- The numerator will encompass all subjects from the denominator reporting the AEI within 7 days following vaccination with a seasonal influenza vaccine derived from the ADR card

95% confidence interval (CI) will be computed on the estimated incidence rates.

Analyses of the secondary objective

All analyses will be carried out overall and by vaccine brand (*Fluarix Tetra* vs. others), by age strata (6 months to 5 years; 6 to 12 years; 13 to 17 years; \geq 18-65 years; $>$ 65 years) and UK CMO-specified risk groups status (at risk/not at risk).

The weekly incidence rates (per 100 subjects) of AEIs within 7 days will be estimated as follows:

- The denominator will be the number of all subjects vaccinated the week before the week of interest (so reaching up to 7 days of follow-up post vaccination during the week of interest)
- The numerator will encompass all vaccinated subjects reporting the AEI within 7 days following vaccination with a seasonal influenza vaccine using data entered in the EHR (i.e., AEIs derived from ADR card and medically attended AEIs)

The cumulative incidence rates (per 100 subjects) of AEIs within 7 days will be estimated as follows:

- The denominator will be the number of all subjects vaccinated at any point from study start up to the week before the week of interest (i.e. cumulatively since the beginning of the study)
- The numerator will encompass all subjects from the denominator reporting the AEI within 7 days following vaccination with a seasonal influenza vaccine using data entered in the EHR (i.e., AEIs derived from ADR card and medically attended AEIs)

95% CI will be computed on the estimated incidence rates.

Analyses of the tertiary objectives

The percentage of subjects vaccinated with a seasonal influenza vaccine during the study vaccination period in the 10 participating GP practices will be tabulated by vaccine brand, age categories and CMO-specified risk groups.

Completeness of seasonal influenza vaccination data in the EHR will be assessed by computing the percentage of subjects with data on influenza vaccines recorded in EHR (date of vaccination, vaccine brand, vaccine batch number).

Timeliness of vaccination data in the EHR will be assessed as follows:

- Time interval in days between the seasonal influenza vaccination dates and the dates at which the records were entered in EHR will be summarized using descriptive statistics (mean, standard deviation, median, range, first and third quartile).

Timeliness of AEI reporting in EHR (medically attended AEs and from the card-based ADR reporting system) will be assessed as follows:

- Time interval in days between the first onset date of AEIs within the 7 days post-vaccination period and the dates at which the records were entered in EHR will be summarized using descriptive statistics (mean, standard deviation, median, range, first and third quartile).

The percentage of subjects who received and who returned the ADR card will be tabulated by vaccine brand.

Sensitive analyses

[figure not shown]
The cumulative incidence rates (per 100 subjects) of AEIs within the 7 days post-vaccination period derived from the ADR card, with 95%CI, will also be tabulated for subjects who returned the ADR card.

The cumulative incidence rates (per 100 subjects) of AEIs within the 7 days post-vaccination period, with 95%CI, will also be tabulated for subjects from the RCGP RSC network of GP practices.

[figure not shown]
Schematic description of process from site selection to data extraction

A series of flow charts have been developed to facilitate understanding of recruitment flow, the training and other process that have to be developed as participating GP practices, and to explain the data flow in the practice.

[figure not shown]
The flow charts are presented below

Flow chart 1: Practice selection process

[figure not shown]
Flow chart 2: Preparation pre-study & site initiation process

[figure not shown]
Flow chart 3: Visits during study linked to data quality

Flow chart 4: Data capture flow chart – patient flu vaccinated in the surgery

[figure not shown]

Flow chart 5: Data capture flow chart – patient NOT vaccinated in the surgery

The added value of combining those two systems is to be able to enhance the collection of AEIs (using the customized cards) and ensure further that the data is comprehensively collected (using the routine EHR system).

Flow chart summarizing the automated data extraction process performed using Apollo system

Safety reporting, including routine pharmacovigilance

Safety reporting

An AE is any untoward medical occurrence in a patient or clinical investigation subject, temporally associated with the use of a medicinal product, whether or not considered related to the medicinal product.

An AEI is any untoward medical occurrence which follows immunisation and which does not necessarily have a causal relationship with the usage of the vaccine. The AEIs following vaccination may be any unfavourable or unintended sign, abnormal laboratory finding, symptom or disease. EMA recommendations regarding AEIs collected after vaccination in this study are specified in Appendix 2.

A Serious Adverse Event (SAE) is defined as any adverse event which is fatal, life threatening, disabling or incapacitating, requires in-patient treatment or prolongs existing hospitalization, is a congenital anomaly in the off-spring of the patient or which may require intervention to prevent the previously stated outcomes.

It will be clearly communicated to participating GP practices that the study does not replace reporting of AEs/SAEs that should occur as part of routine practice as specified by their local regulations. GPs should continue to report any AEs/SAEs they would typically report using the mechanisms routinely used in their GP practices. Therefore, although the data collected for this study

is primarily safety-related, reporting mechanisms of AEs to regulatory authorities should not be altered and is to continue according to each practice's standards.

In addition, if the team at the University of Surrey becomes aware of an SAE experienced by a study participant that is deemed to be related to a GSK flu vaccine, the SAE should be reported to GSK within 24 hours of awareness using the GSK reporting forms (forms are provided in the contract agreement). If GSK deems additional information necessary, request of additional information will be sent through the team at the University of Surrey.

Study Contact for Reporting SAEs
GSK Biologicals Clinical Safety & Pharmacovigilance
Fax: +PPD [REDACTED] or PPD [REDACTED]
Email: PPD [REDACTED]

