The recruitment will be performed by GP practice and this might create a clustering effect. Based on the previous year study (EPI-FLU-046 study) the clustering effect is expected to be negligible. Similarly to last year, in the present study, the clustering effect was not accounted for in the power calculation but will be considered during the analysis.

Cluster effect

Cluster effect requires special statistical considerations when designing the study, and later when analysing the data. Groups tend to form because of certain selection factors, so individuals within the group tend to be more similar to each other with respect to important potential confounders than those selected truly at random.

For instance, patients medically followed by the same GP are usually more prone to receive similar treatment for a given condition than those being treated for the same condition by different physicians. Furthermore, patients attending a single GP practice are likely to share similarities including geography, socioeconomic status, ethnic background, or age by virtue of the area they have all chosen to live in the same way. GPs who have chosen to work together are likely to share similarities.

Similarities, or homogeneity, between subjects in clusters reduces the variability of their responses, compared with that expected from a random sample. As a consequence, a compensatory increase in sample size is required to maintain power in studies characterised by a cluster effect and the degree of similarity of within clusters should also be assessed. The intra-cluster correlation coefficient (ICC) is a measure of the relatedness or similarity of clustered data. There are different methods of calculating the ICC, usually requiring a pilot study, but all compare the variance within clusters with the variance between clusters.

Sample size calculation

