7.3.2. Analyses of primary objectives

The weekly incidence rate (per 100 subjects) of any AEIs within 7 days* post-vaccination period reported via ADR card will be estimated by Vaccine group as follows in the Weekly vaccinated cohorts restricted to subjects who received the ADR card:

- The denominator will be the number of subjects in the Weekly vaccinated cohort for the week of interest who received the ADR card
- The numerator will be the number of subjects from the denominator who reported any AEIs on the ADR card within 7 days following vaccination with the seasonal influenza vaccine

**Day of vaccination plus the following 7 days*

The cumulative incidence rate (per 100 subjects) of any AEIs within 7 days post-vaccination period reported via ADR card will be estimated by Vaccine group as follows in the Cumulative vaccinated cohorts restricted to subjects who received the ADR card:

- The denominator will be the number of subjects in the Cumulative vaccinated cohort up to the week of interest who received the ADR card
- The numerator will be the number of subjects from the denominator who reported any AEIs on the ADR card within 7 days following vaccination with the seasonal influenza vaccine

Similarly, weekly and cumulative incidence rates will be estimated for the following AEIs within 7 days post-vaccination period reported via ADR card:

- Fever/pyrexia
- Fever $>38.5^{\circ}\text{C}$ and $>39.5^{\circ}\text{C}$ (with a temperature measurement recorded in EHR; independent of route of measurement)
- Local symptoms (i.e. local erythema)
- Any and each general non-specific symptom: drowsiness, fatigue, headache, irritability and malaise
- Any and each respiratory AE: conjunctivitis, coryza, cough, epistaxis, hoarseness, nasal congestion, oropharyngeal pain, rhinorrhoea, wheezing
- Any and each gastrointestinal AE: decreased appetite, diarrhea, nausea, vomiting
- Any and each sensitivity/anaphylaxis AE: anaphylactic reactions, facial oedema, hypersensitivity reactions
- Rash
- Any and each musculoskeletal AE: arthropathy, muscle aches / myalgia
- Any and each neurological AE: Bell's palsy, Guillain-Barre syndrome, peripheral tremor, seizure / febrile convulsions

Similarly, weekly and cumulative incidence rates of any SAEs within 7 days post-vaccination period reported via ADR card will also be generated.

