In addition, weekly and cumulative incidence rates of any AEIs, each AEIs category (i.e. fever/pyrexia, local symptoms, any general non-specific symptom, any respiratory, any gastrointestinal, any sensitivity/anaphylaxis, rash, any musculoskeletal and any neurological AEs) and SAEs within 7 days post-vaccination period reported via ADR card will also be generated by Age group (6 months to 5 years; 6 to 12 years; 13 to 17 years; 18-65 years; >65 years) and by UK CMO-specified risk status (at risk, not at risk).

95% confidence interval (CI) adjusted for clustering effect of GP practices will be computed on all estimated incidence rates (Clopper-Pearson exact CI modified for cluster data as described in [Annex 1](#)).

The design effects and the intra-cluster correlation coefficients will also be estimated as described in [Annex 1](#) for the estimated cumulative incidence rates of AEIs reported on the ADR card within the 7 days post-vaccination period for the Cumulative vaccinated cohort Weeks 35-48 restricted to subjects who received the ADR card.

7.3.3. **Analyses of secondary objectives**

All analyses described for the primary objectives (refer to Section [7.3.2](#)) will also be generated by Vaccine group for all subjects included in the Weekly vaccinated cohorts and the Cumulative vaccinated cohorts (i.e. whether or not they received the ADR card).

For the weekly incidence rates (per 100 subjects):

- The denominator will be the number of subjects in the Weekly vaccinated cohort for the week of interest
- The numerator will be the number of subjects from the denominator who reported the specified AEI within 7 days following vaccination with the seasonal influenza vaccine using data entered in the EHR (i.e. AEIs derived from ADR card and medically attended AEIs)

For the cumulative incidence rates (per 100 subjects):

- The denominator will be the number of subjects in the Cumulative vaccinated cohort up to the week of interest
- The numerator will be the number of subjects from the denominator who reported the specified AEI within 7 days following vaccination with the seasonal influenza vaccine using data entered in the EHR (i.e. AEIs derived from ADR card and medically attended AEIs)

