12. ANNEX 1 STATISTICAL METHODS AND DATA DERIVATION RULES

12.1. Statistical Method

The recruitment will be performed by the GP practices and this may create a clustering effect.

Subjects medically followed by the same GP practices are more prone to receive similar treatment for a given condition than those being treated for the same condition by different physicians. Furthermore, subjects attending a single GP practice are likely to share similarities including geography, socioeconomic status, ethnic background, or age by virtue of the area in which they have all chosen to live. In the same way, GP practices which have chosen to work together are likely to share similarities.

Similarities (or homogeneity) between subjects in clusters reduce the variability of their responses, compared with that expected from a random sample. Not accounting for cluster effect would overestimate the precision of the estimated rates.

The two-sided 95% CI for a proportion within a group accounting for clustering effect will be estimated using the Clopper-Pearson exact CI modified for cluster data [Korn, E.L. and Graubard, B.I. (1998). Confidence Intervals for Proportions with Very Small Expected Number of Positive Counts Estimated from Survey Data. *Survey Methodology*, 24, 193–201].

The design effect (DE), assessing the impact of clustered data on the variance, will be estimated as follows (PROC SURVEYFREQ in SAS with CLUSTER statement):

DE = actual variance (estimated using Taylor series linearization method) over the variance of a simple random sample with the same number of observations

The intra-cluster correlation (ICC) will be estimated as follows:

$$ICC = (DE-1) / (m-1)$$

Where DE is the design effect and m is the average number of subjects per cluster

The exact two-sided 95% CI for a proportion within a group not accounting for clustering effect will be calculated using the method described in Clopper-Pearson exact CI [Clopper CJ, Pearson ES. The use of confidence or fiducial limits illustrated in the case of binomial. *Biometrika*. 1934;26:404-413].

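### Do Tables 1 and 2 overstate precision because they ignore clustering and count all vaccinees?

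*Protocol*

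**What the plan says.** Protocol section 5 (Sample size consideration) expects up to 5,000 vaccinated subjects from 10 practices, with a regulatory minimum of 1,000. Tables 1 and 2 give exact binomial limits, the RSE and the probability of at least one adverse event of interest (AEI), for 1,000 to 10,000 vaccinees.

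On clustering the protocol states "Based on the previous year study (EPI-FLU-046 study) the clustering effect is expected to be negligible", and that "the clustering effect was not accounted for in the power calculation but will be considered during the analysis". Under Cluster effect it adds that "the degree of similarity of within clusters should also be assessed" and remarks: "There are different methods of calculating the ICC, usually requiring a pilot study". No ICC or DE appears in either document.

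SAP section 7.3.2 defines the primary weekly rate on card recipients: "The denominator will be the number of subjects in the Weekly vaccinated cohort for the week of interest who received the ADR card". It also specifies: "95% confidence interval (CI) adjusted for clustering effect of GP practices will be computed on all estimated incidence rates". For the cumulative card-based rates over the whole period, "The design effects and the intra-cluster correlation coefficients will also be estimated". SAP 12.1 gives the method (the Korn-Graubard modification of Clopper-Pearson) and the reason: "Not accounting for cluster effect would overestimate the precision of the estimated rates". SAP 7.3.6.1 keeps the unadjusted interval as a sensitivity analysis. SAP sections 8 and 9.2 make the study descriptive, without hypothesis tests.

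**The concern.** The planned precision and the reported interval are different quantities. The tables use all vaccinees and DE = 1. The primary interval uses card recipients and whatever DE the 10 practices produce. With about 500 vaccinees per practice, even a very small ICC inflates the variance noticeably, so calling the effect negligible needs a number behind it. The protocol says an ICC usually comes from a pilot study. It had one in EPI-FLU-046, yet quotes no value.

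The tables are also the only place where the documents quantify how certain an estimated rate would be. If they were too optimistic, readers would expect narrower intervals than the study can deliver.

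Two smaller oddities add to the impression. Table 2 spreads uptake over 14 equal weeks, although 1 September to 30 November is 91 days, or 13 full weeks. And one Table 1 probability (1,000 vaccinees, 0.06%) reads 43.13%, where the formula gives 45.13%.

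**Working it through.** **Inputs.** n = 5,000 expected vaccinees, minimum 1,000, and 10 practices (protocol, Sample size consideration); p = 1% (Table 2, and a row of Table 1); ICC = (DE − 1)/(m − 1) with m the mean cluster size (SAP 12.1), so DE = 1 + (m − 1) × ICC. The ICC and the share of vaccinees given a card are not in the documents; all values below are assumptions, with practices taken as equal in size.

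**1. Reproduce the stated figure.** RSE = √((1 − p)/(np)) = √(0.99/50) = 14.1%. Clopper-Pearson on 50/5,000 gives 0.74% to 1.32%. Table 1 prints 14.1% and 0.7% to 1.3%. The match confirms DE = 1 and n = all vaccinees.

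**2. Add clustering.** With m = 5,000/10 = 500, RSE = 14.07% × √DE, and the limits are Clopper-Pearson on n/DE:

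| Assumed ICC | DE | n/DE | RSE | 95% CI |
|---|---|---|---|---|
| 0 | 1.00 | 5,000 | 14.1% | 0.74–1.32% |
| 0.001 | 1.50 | 3,336 | 17.2% | 0.69–1.40% |
| 0.002 | 2.00 | 2,503 | 19.9% | 0.65–1.47% |
| 0.005 | 3.50 | 1,431 | 26.3% | 0.55–1.66% |

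A degrees-of-freedom correction for 10 practices would widen these a little: if the Korn-Graubard adjustment uses 9 df, the ICC 0.001 interval becomes 0.65–1.47%.

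**3. Compare with rows already in Table 1.** At 1%, the 2,500 row (RSE 19.9%, CI 0.6–1.5%) is 5,000 vaccinees at DE = 5,000/2,500 = 2, so ICC = 1/499 = 0.002. The 1,000 row (RSE 31.5%, CI 0.5–1.8%) is DE = 5,000/1,000 = 5, so ICC = 4/499 = 0.008. The tabulated range therefore reaches beyond every case in step 2.

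**4. Card recipients.** If 90% or 70% of 5,000 receive a card, RSE at ICC 0 is √(0.99/45) = 14.8% or √(0.99/35) = 16.8%. The roughly 50% return rate from EPI-FLU-046 does not apply here: subjects who receive but do not return a card stay in the primary denominator (SAP 7.3.2 and 12.2.4).

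**5. Early weeks.** At 357 vaccinees (week 1, 10% coverage), m = 35.7. DE is 1.035 at ICC 0.001 and 1.174 at ICC 0.005, so the RSE rises by factors of √1.035 = 1.017 and √1.174 = 1.083. Near-real-time monitoring is barely affected.

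**6. Probability of at least one AEI.** This is the other stated purpose of the tables. With a beta-binomial for 10 equal practices and ICC 0.005, p = 1% gives >99.99% at 5,000 and 99.97% at 1,000. For rarer events it does fall: at 0.1% and 5,000, from 99.3% to 98.3% (ICC 0.001) or 91.8% (ICC 0.005).

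**7. The smaller oddities.** SAP Annex 4 lists ISO weeks 35 to 48, which is 14 calendar weeks with short ends: 3 + 12 × 7 + 4 = 91 days. For the Table 1 cell, 1 − 0.9994^1000 = 45.13%. The RSE in the same row, √(0.9994/0.6) = 129.1%, is printed correctly.

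**The case for a change.** The strongest case for a change is that the protocol itself says clustering deserves attention at the design stage, then relies on a prior-season result it does not report. Keeping the RSE within 10% of its stated value at 5,000 vaccinees requires DE ≤ 1.1² = 1.21, hence ICC ≤ 0.21/499 = 0.0004. That is a demanding threshold for a claim resting on one sentence. The table rows are labelled by vaccine coverage, so a reader is not told that a lower row can stand in for a DE.

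This stands as a remark on reporting: the claim cannot be verified from the documents. It does not show that the precision is wrong. Every clustered figure above rests on an assumed ICC, and the prior-season estimate may well meet the threshold. The study size also does not rest on the tables alone, since the minimum of 1,000 comes from the regulatory request. The planning figures have slack too: about 70,340 registered patients were expected but 50,000 used, and coverage of 2–20% was tabulated against quoted uptake of 42.3–71.0% in target groups.

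The two oddities add nothing. Fourteen is a fair count of calendar weeks, and equal accrual is a planning scenario; replacing it with even daily uptake would be another assumption, and practices start vaccinating at different times. The 43.13% cell enters no stated range. It may be a 5 read as a 3 when the text was taken from the PDF: the code lists show the same pattern, with 165.. and SN501 in protocol Appendix 2 but 163.. and SN301 in SAP Annex 2.

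**Conclusion.** No change to enrolment or analysis is warranted. The tables do describe independent subjects and all vaccinees, while the primary interval will be clustered and limited to card recipients. But the protocol discloses the clustering omission with a reason, and the SAP deals with it where it counts: in the intervals, in the estimated DE and ICC, and in an unadjusted comparison. Readers of the final report will see the actual precision.

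If the unquoted ICC were 0.002, the RSE at 5,000 vaccinees and 1% would be 19.9% instead of 14.1%; at 0.005 it would be 26.3%. Both lie within the span of the existing rows, and with no hypothesis test they affect expectations about interval width, not any decision rule. These sizes assume 10 equal practices, cards issued to all vaccinees as both documents intend, and ICC values the documents do not give. Stating that the tables assume DE = 1 and all vaccinees, and quoting the EPI-FLU-046 estimate, would help a reader but would alter no result or conclusion.
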